After completing the inpatient phase of the study, subjects will either taper off the study medication or participate in a 9-week outpatient medication trial. Those choosing to continue treatment will be seen 2 times per week in outpatient treatment at the Substance Abuse Center at CMHC, or at the Yale Stress Center at [name]. Subjects will be maintained on 16.0mg dose of PRZ/PLA until week 12. In week 12, subjects will undergo a 5-day taper similar to what has been used with Lofexidine in opiate withdrawal protocols (Bearn et al., 1996; Strange et al., 1997) and in our outpatient relapse prevention study of Lofexidine and Guanfacine with opiate and cocaine dependent patients respectively. Urine monitoring, assessment of craving, alcohol abstinence symptoms, self report of drug use and stress and craving scales, heart rate and blood pressure will be assessed weekly in the trial.

Inpatient-Outpatient Plan without laboratory sessions:

The plan for subjects completing the Inpatient-Outpatient Plan without laboratory sessions, will be identical to the plan for the Inpatient-Outpatient Plan with laboratory sessions, minus the laboratory sessions, and all procedures related to the laboratory sessions, such as participating in imagery script development sessions. Once a subject is deemed eligible, those who are interested in the inpatient option will be admitted to the Clinical Neuroscience Research Unit (CNRU) of

the Connecticut Mental Health Center (CMHC) for the 3 - 4 week stay that will involve medication initiation.

After completing the inpatient phase of the study, subjects will either taper off the study medication or participate in a 9-week outpatient medication trial. Those choosing to continue treatment will be seen 2 times per week in outpatient treatment at the Substance Abuse Center at CMHC, or at the Yale Stress Center at [name]. Subjects will be maintained on 16.0mg dose of PRZ/PLA until week 12.

Outpatient Plan:

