During the physical, 8ml of whole blood will also be drawn to analyze molecular adaptations. Microarray profiling will be used to detect these molecular changes by comparing the molecular profile of the blood drawn during the physical to another 8ml of blood drawn during one of the laboratory sessions. A total of 16ml of whole blood will be drawn to examine molecular changes in the blood.

During the physical, all female subjects will have 8ml of whole blood drawn to determine estradiol levels. Estradiol levels drawn during the physical will be compared to another 8ml of blood drawn during one of the laboratory sessions. A total of 16ml of whole blood will be drawn to measure estradiol levels.

Laboratory Sessions:

Rationale for Use of Personalized Imagery Procedures. Emotional imagery paradigms have been widely used in behavioral research studies examining the pathophysiology of anxiety disorders, including panic disorder, obsessive compulsive disorder and PTSD (Cook, Melamed, Cuthbert, McNeil, & Lang, 1988; Foa & Kozak, 1986; McNeil, Vrana, Melamed, Cuthbert, & Lang, 1993; Pitman, Orr, Foa, de Jong, & Claiborn, 1987; Shalev, Orr, & Pitman, 1993; Orr et al., 1998; Orr, Pitman, Lasko, & Herz, 1993). These procedures are known to activate the same physiological, subjective and behavioral components as the emotion trigger situations, thus being a useful clinical research procedure for inducing stress/emotional states. Similar imagery induction procedures have been successfully adapted by our group in previous studies to induce specific emotion states in normal volunteers and stress and alcohol cues in alcohol dependent individuals (Sinha, Lovallo, & Parsons, 1992; Sinha & Parsons, 1996; Sinha, Catapano, & O'Malley, 1999a; see Preliminary Studies section C1, C2, C6).

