Imagery and Relaxation Training and IV Habituation Day- STUDY DAY 1. On the afternoon of DAY 1, an indwelling catheter will be inserted in the subject’s arm for one hour, so that subjects can habituate to the stress of an IV insertion. We have found that this period of adaptation is critical for stable baseline measurements on testing days. No blood will be drawn on the training day. After insertion of IV catheter, the subject will be provided with relaxation training followed by general imagery and physiological response training, as described in the imagery training procedures manual (Lang, Levin, Miller, & Kozak, 1983). The imagery training involves subjects' visualizing some commonplace scenes as they are presented to them. The scenes are neutral and non-emotional in content, such as reading a popular magazine. Following the imagery, the subject is asked questions about the visualization and given pointers regarding the process of imagining the scene. The subject also imagines scenes that are non-emotional but physically arousing in nature, such as doing sit-ups in gym class. With these scenes subjects are asked whether they notice any changes in their physiological response, such as change in heart rate or change in breathing. Once again, pointers with regard to imagining the situation "as if" they were really present in the situation are presented. This session takes approximately one hour and was developed to insure that all subjects are trained on the method of generating an image and maintaining it for 2-3 minutes.

Laboratory Sessions. On DAY 2, 3, and 4 of the study, subjects will be brought into the research testing rooms of the CNRU at 8:00 AM after a smoke break at 7:30 AM. Breakfast will be withheld from the subject until after the laboratory session. The subject will then be prepared for physiological assessments. An indwelling intravenous (IV) catheter will be inserted by the research nurse specialist in the antecubital region of the subject's non-preferred arm for blood sampling. Blood samples will be obtained periodically for assessment of ACTH, cortisol, prolactin, NE and EPI levels. A blood pressure cuff will be placed on the subject's preferred arm to monitor blood pressure (BP) periodically. On-line assessment of physiological measures will be obtained at specified time periods during the laboratory sessions. Self-reports of emotional state, anxiety and alcohol craving will also be assessed periodically.

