After preparation of assessments and a 40 minute adaptation period, a –20 minutes and –5 minutes blood draw will be conducted. After the –5 blood draw, a 5-minute baseline period will follow to assess continuous pulse rate and BP assessments. Following the baseline period, instructions for conducting imagery will be provided. The order and content of the imagery condition will not be revealed to the subject or to the research staff conducting the sessions. In the imagery task the subjects will be asked to imagine the situation being described vividly, 'as if he/she is in the specific situation and actively participating in it, until asked to stop. The imagery script will be played to the subject over headphones and the subject will be required to imagine the situation for 5 minutes. A tape recording for each subject's script will be developed prior to the testing situation and read by the same person for each subject. Timeline for assessments are summarized in Table 3.

TABLE 3: Schedule for Laboratory Sessions

DAY 1:	Imagery and Relaxation and Habituation Session (1 hour)
DAY 2, 3 and 4:	IMAGERY SESSIONS
8:00 AM	Set-up for plasma (IV insert) measures; physiological setup - HR, BP
8:10 AM	Stabilization and Adaptation period, BP reading
8:40 AM (-20)	Initial Blood Draw, craving/DES ratings, physiological assessments
8:50 (-10)	BASELINE Period; on-line physiological recordings
8:55 (-5)	Baseline blood draws; craving/DES ratings, BP assessments
9:00	IMAGE Period (Stress/Drug Cues/Neutral); physiological assessments
9:05 (0)	Post-Image blood draw; craving/DES ratings; Imagery Vividness ratings
9:10 (+5)	RECOVERY Period; 5-min physiological assessments; craving/DES ratings;
9:20 (+15)	Recovery1: Blood draws, craving/DES ratings; 5 minute physiological assessments
9:35 (+30)	Recovery2: Blood draws, craving/DES ratings; physiological assessments
9:50 (+45)	Recovery3: Blood draws, craving/DES ratings; physiological assessments
10:05 (+60)	Recovery4: Blood draws, craving/DES ratings;
10:20 (+75)	Recovery5: Blood draws, craving/DES ratings; physiological assessments
10:30 AM	Relaxation tape; assess physiological levels and subjective state for return to baseline

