 - G. Describe the methods for the security of storage and sharing of materials

Thirty-two cc's of whole blood will be collected from patients during day 1 of the laboratory sessions for the purposes of understanding genetic factors that may influence the way in which the subject behaves/feels in response to alcohol. For subjects completing the outpatient plan, this blood draw will be done at their intake appointment. Samples will be marked only by study ID numbers and no other personal identifying information will be sent to the laboratory. Once genetic analysis are conducted the data will be sent back to our laboratory and the genetic data will be stored in computerized research records that will then be analyzed by group analysis. There is no plan to return specimens back. If the subject chooses to withdraw their sample, the subject will be informed that the genetic blood sample will be stripped of all identifiers (anonymized) including study id number.

No immortalization of cell lines, animal studies or whole exome or genome sequencing is/are currently planned. Samples are stored in a de-identified sense, and candidate genes will be explored to assess treatment response to prazosin. We have no current funding to conduct genetic analysis. All treatment outcome data are de-identified and there is no way to link subject PHI to genetic or clinical outcome data. Samples may also be contributed to the NIH data bank for analysis of treatment response. Individual level donor's personal health information will not be included; race, gender, age and education level are the only variables included but these do not provide individual level information, but rather are aggregated as group level data.

The sharing of materials and/or distributing for future research projects is limited to contributing to the NIH data bank, as NIH is the funding source. Individual level donor's personal health information will not be included; race, gender, age and education level are the only variables included but these do not provide individual level information. Widespread sharing of materials is not planned.

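### Inpatients give the genetic sample only if they choose and reach the laboratory sessions, after randomisation and on study drug, whereas outpatients give it at intake; the stated draw day is also ambiguous

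*Combined protocol and SAP*

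**What the plan says.** Section V, item 4 (Genetic Testing) says that 32 cc of "whole blood will be collected from patients during day 1 of the laboratory sessions". It then makes one exception: "For subjects completing the outpatient plan, this blood draw will be done at their intake appointment". The Outpatient Plan paragraph in Section V, item 3 also places the draw at intake. One stated use is that "candidate genes will be explored to assess treatment response to prazosin"; the same item and the Outpatient Plan also mention response to alcohol and craving.

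The paragraph on imagery training and IV habituation (Study Day 1) says "No blood will be drawn on the training day". Table 3, the laboratory schedule, likewise gives Day 1 to that training session and lists no draw for it. The Admission text applies the term laboratory sessions to Study Days 2, 3 and 4.

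The sessions are optional for inpatients. Those who do without them follow the same plan "minus the laboratory sessions, and all procedures related to the laboratory sessions". No other genetic draw is stated for them.

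**The concern.** Genotype does not change over time, so the date of the draw does not affect the measurement. What matters is who is still there to be sampled. Randomisation makes genotype independent of treatment arm among all randomised subjects. If DNA is taken only from those who stay, tolerate the drug and remain sober until the sessions, that independence is no longer guaranteed in the sampled subset, because arm and genotype may each affect who gets that far. A comparison of prazosin response by genotype could then be biased, and subjects who did badly early would be under-represented in a sample meant to explain response. The sampling rule would also differ between the two plans.

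The second matter is practical. Read against Table 3, the genetic draw falls on the one day of the laboratory block when no blood is to be taken, so staff cannot tell from the text when to take it.

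**Working it through.** No power or sample-size figure is involved. The check is a comparison of the relevant sections, with one sum.

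**Who is sampled, and when**

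| Plan | Genetic draw | Relation to treatment |
|---|---|---|
| Outpatient, with or without sessions | Intake (Genetic Testing; Outpatient Plan) | Before randomisation, in the order given at the start of the Research Plan |
| Inpatient-outpatient with sessions | First day of the sessions (Genetic Testing) | After randomisation, on study drug |
| Inpatient-outpatient without sessions | None stated | Not applicable |

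**What an inpatient must pass before giving DNA**

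1. Choose the sessions. The Research Plan makes them optional.
2. Stay through titration. The Admission text starts the session block at week 3 or day 15, and the titration schedule reaches the full dose on day 14.
3. Meet a sobriety condition: at least 14 days in the Admission text, 21+ days in the Research Plan.

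Steps 2 and 3 come after randomisation and can depend on arm. Two other rules bear on them. The Research Plan removes subjects who cannot tolerate a minimum dose, and the Prazosin Treatment risk text stops medication if drinking resumes.

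**Can the size be computed?** Let p be the share of randomised subjects in the outpatient plan, u the share of inpatients who choose the sessions, and r the share of those who reach them. Taking outpatient coverage as complete:

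- DNA coverage of the whole trial = p + (1 − p) × u × r
- DNA coverage of inpatients = u × r

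Only r is clearly determined after treatment starts. The documents give none of p, u or r. The 15-20% drop-out in the power analysis is an allowance for the whole trial after enrolment, so it is not an estimate of 1 − r.

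**Does the blood total show which day is meant?** Table 3 lists 8 draws per session (−20, −5, 0, +15, +30, +45, +60 and +75 minutes), at 15 ml each:

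- per session: 8 × 15 = 120 ml
- three sessions: 3 × 120 = 360 ml
- whole study: 360 + 32 + 16 + 16 = 424 ml

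This reproduces the total in the Drawing of Blood risk text. The 32 ml is added outside the sessions' 360 ml, and Table 3 shows it on no day, so the sum cannot settle the reading.

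**The two readings of day 1.** By Table 3, day 1 is the training day, when no blood is drawn, and the texts conflict. By the Admission text, the first laboratory session is Study Day 2, when blood is drawn, and there is no conflict. On both readings the inpatient draw comes after treatment has started and only in those who reach the sessions.

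**The case against.** The strongest reply is that nothing planned depends on this. The Genetic Testing heading is marked not applicable, the text says there is no current funding for the analysis, and genetics appears in no aim, hypothesis, outcome or model in the Statistical Considerations. That stands, and it limits the severity.

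Some stronger readings are tempting, but the documents do not support them.

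- A reader might infer that the whole gene sample is selected after treatment starts. It is not: outpatient-plan subjects give theirs at intake, whether or not they later do the sessions.
- A reader might infer a flat order to draw blood on a no-blood day. The Admission text allows Study Day 2, so this may be only a labelling fault.
- A reader might infer that an extra 32 ml disturbs one session. Nothing in the documents shows this. The Physiological Assessments text already adds 8 ml draws during one of the sessions, and imagery order is counterbalanced across subjects.
- A reader might infer that every inpatient who relapses, leaves or cannot tolerate the full dose lacks DNA. Only losses before the sessions count. Later drop-outs among session-takers have already been sampled, and subjects who do not tolerate 16 mg may continue on less.
- A reader might count all inpatients without sessions as lost because of treatment. They have their own consent form, which suggests that many choose at enrolment. Such a choice cannot depend on response to the drug, although it still leaves their DNA uncollected.

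One further point softens the selection. Inpatients live on the unit and have urine checks three times weekly, so for them the sobriety condition may amount largely to staying in. That is an inference, and retention can itself differ by arm.

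**Conclusion.** The point holds in a limited form. The genetic sample is mixed: outpatients before treatment, inpatients after it starts and only if they choose and reach the sessions, and inpatients without sessions not at all as the text stands. For the inpatient stratum, a sample meant to study prazosin response therefore depends partly on what happened after randomisation. The draw day also needs to be reconciled with Table 3 and the Study Day 1 text.

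The direction and size of any bias are unknown. They depend on the plan split, on session uptake, and on whether reaching the sessions differs by arm and genotype; the documents give none of these. The conclusion assumes that the Genetic Testing item means what it says for inpatients and that no unstated intake draw exists for them. It does not touch the trial's primary or secondary outcomes. It is worth correcting because DNA not taken early cannot be recovered reliably from subjects who leave, and because the samples may also go to the NIH data bank, where the same selection would follow them.

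**What to change.** In Section V, item 4, replace the sentence that sets the draw on the first laboratory day, and the outpatient exception after it, with: *The 32 cc sample for genetic analysis is drawn at the intake physical, before randomisation and before the first dose of study medication, from all subjects in every plan.*

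This extends to inpatients what outpatients already do. Blood is already taken at that visit: "During the physical, 8ml of whole blood will also be drawn to analyze molecular adaptations". The change removes the post-randomisation selection, the gap for inpatients without sessions and the day-1 ambiguity together. It leaves the 424 ml total unchanged for those who complete the sessions.

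Check that the consent form for inpatients without laboratory sessions, listed in Section VII, item 11, covers a genetic sample, and amend it if not. The consent pages are not available here, so this could not be verified.

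The cost is one amended protocol statement and possibly one consent amendment. Inpatients who skip or never reach the sessions would also give 32 ml, and more samples would be stored. If samples have already been collected under the present text, any report of gene and treatment response should state how many randomised subjects gave DNA, by plan and arm.

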All subjects will also be seen two times per week in outpatient treatment at the Yale Stress Center. All subjects will participate in 1x per week standard individual drug counseling as outlined in the Individual Drug Counseling Manual (IDC, Mercer & Woody, 1998) during the outpatient trial. Each subject will be assigned a counselor with expertise in IDC. The general purpose of the counseling sessions as described in the manual are to: (1) acquire information about important concepts and aspects of recovery from addiction; (2) increase self-awareness of specific problems and issues in relation to addiction and recovery, and (3) learn new coping skills to deal with problems contributing to or resulting from the addiction and to improve functioning. The focus of this psycho-educational approach is on providing patients with frequent supportive contact, introduce them to key concepts about the recovery approach, and develop a sense of personal responsibility for recovery.

Relapse in the pilot study will be defined as the first day of any alcohol use as documented by self-report and/or positive urine and positive breathalyzer for alcohol. Treatment drop-out is defined as four consecutive missed research appointments for medication self-administration. Relapse to alcohol will be recorded in the data and subjects will continue in the protocol. Furthermore, it will be addressed by their counselor and doctor in therapy appointments. If subjects have missed four consecutive appointments, all attempts will be made to bring the subject back and after a full assessment of the subject's need, a formal referral will be made to appropriate residential, inpatient or intensive outpatient care. Subjects will be maintained in regular treatment until they have entered treatment at the next appropriate level of care. Other clinical deterioration such as exacerbation of psychiatric or withdrawal symptoms will be assessed on a case-by-case basis by the study investigators. When clinically indicated and necessary, psychotropic medication or discontinuation of study medication will be initiated and/or a referral will be made to intensive outpatient, residential or inpatient care.

Physiological Assessments

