Alcohol Dependence Scale (ADS) is a 25 item to measure severity of alcohol dependence; the Alcohol Use Questionnaire (AUQ) consists of 8 items to determine the respondent's alcohol craving; Smoking History Questionnaire

Abstinence Measures:

Clinical Institute Withdrawal Assessment-Alcohol Revised (CIWA-Ar) is a 13 item scale that measures alcohol withdrawal signs and symptoms. The assessment will be administered at intake and weekly.

Urine Toxicology and Breathalyzer Screening: A urine toxicology screen will be conducted at intake to confirm alcohol use. During treatment, urines will be collected 3 times weekly to confirm sobriety during inpatient stay using the CNRU laboratory. In addition, urine samples will be taken 2 times weekly during outpatient treatment and at follow-up appointments using on-site TESTCUP5 Drug Screen (Roche Diagnostics Inc., Totowa, NJ) to monitor opiate and other drug use. The TestCup5 kit provides results for opioids, cocaine, THC, PCP and barbiturates. In addition, breath alcohol levels will also be assessed with the Alcosensor III Intoximeter at each face-to-face contact, 2 times weekly.

Assessment of Psychological Symptoms:

A number of self report measures of psychological functioning will be obtained weekly to examine Prazosin's effects on psychological functioning. The following well-established and reliable instruments will be used:

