with medication and alcohol withdrawal/anxiety, we used a conservative effect size of $d = .60$ for detection of significant main effects and possible interactions in the clinical trial. At this effect size and power = .80, with $p < .05$, sample size estimates from Cohen (1988, p.258) indicated that we would require 25 subjects per cell to adequately assess the proposed hypotheses for the clinical trial (total $N = 100$). Including a 15-20% drop-out after enrollment, we estimated recruitment of 120 AD patients into the trial to ensure adequate power for the trial.

Data Analysis for Laboratory Study: Repeated measures ANOVA and mixed model procedures to assess treatment group differences in alcohol craving and stress related changes (heart rate, blood pressure, HPA and catecholamine responses) during laboratory exposure to stress and drug cues as compared to neutral imagery conditions. Non-parametric tests will be used to assess occurrence of side effects, treatment retention rates, alcohol use measures, CIWA scores and perceived stress scores during the outpatient treatment phase. The number and type of AE's for the two treatment groups will be conducted using t-tests, chi-square tests and ANOVAs as appropriate. Findings will be used to estimate effect sizes for the medication and guide the larger randomized clinical trial.

Data Analysis for the 12-week clinical trial Study: For this phase, the following moderator and primary and secondary outcomes are specified:

Primary Moderator Measure: Alcohol withdrawal symptoms, as measured by the CIWA alcohol withdrawal scale,

Primary Outcome Measures in the outpatient treatment phase: These are: (1) Heavy drinking days (5 or more for men, 4 or more for women) during the 12 week period, and (2) Any drinking days. Both will be assessed daily using smartphone or interactive voice recording surveys completed by the patients and also with weekly urine drug screens/breathalyzer reports and self report of drug use on the Substance Use Calendar.

Secondary Outcome Measures in the outpatient treatment phase: Secondary outcome measures will include alcohol craving scales, anxiety (Hamilton Anxiety Scale) and depression (CES-D) and sleep quality using the Pittsburgh Sleep Quality Index – PSQI).

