Outpatient subjects will come in for 2x weekly appointments and complete motivational enhancement, urine drug screens, breathalyzers, blood pressure monitoring, and counseling. Medication compliance will be monitored by blood draws done at week 4-5, to measure Prazosin levels, and through the monitoring of riboflavin as a urine marker. Riboflavin produces a bright yellow discoloration of the urine when the medication is taken 2 to 8 hours prior. After the first week all subjects will be taking morning and bedtimes doses of the medication. After this time, staff will easily be able to visually inspect the subject's urine to determine whether the morning

dose has been taken. 25mg of riboflavin will be added to all doses of Prazosin and placebo by the pharmacist when capsules are made.

Outpatient subjects will self-administer study medication, and will be reminded via daily interactive voice response (IVR) telephone monitoring or through the smartphone app MetricWire. Daily IVR telephone monitoring or MetricWire will be used to prompt patients to take study medication, and also to assess alcohol use, craving, craving resistance and mood states. Concordance between daily IVR or MetricWire reports and alcohol positive urines will be evaluated for daily versus retrospective reporting.

The MetricWire app (developed and owned by MetricWire Inc), has previously been utilized in clinical and academic research, and is HIPPA compliant. Subjects will complete a training session where we will assist them in installing the app on their smartphone device. At the end of the study, we will assist subjects in removing the app from their smartphone. If a subject does not own a smartphone, one will be supplied for their use, for the duration of the study, once a separate smartphone agreement is understood and signed.

We expect most subjects will tolerate a dose of 16mg. However, subjects who cannot tolerate a dosing schedule of 16mg will meet with the study psychiatrist to discuss a lower dose. Subjects who cannot tolerate a minimum dose of 16mg will be maintained on maximum tolerated dose of Prazosin (up to 16.0 mg/day) and during week 12 the medication will be tapered down to 0 over the course of seven days. Some patients may be tapered prior to week 12.

All study staff will remain blind to medication condition. Randomization will be conducted by the CMHC Pharmacy / YNHHS IDS, which have extensive experience in random assignment of patients in medication trials.

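### The outpatient urine kit lists no alcohol test, so for outpatients the urine concordance analysis cannot be run and the biochemical limb of the relapse definition cannot be met

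*Combined protocol and SAP*

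**What the plan says.** Section V.3, under Urine Toxicology and Breathalyzer Screening, describes three urine settings and one breath test.

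- **Intake:** "A urine toxicology screen will be conducted at intake to confirm alcohol use". The assay is not named.
- **Inpatient:** "urines will be collected 3 times weekly to confirm sobriety during inpatient stay using the CNRU laboratory". The analytes are not listed.
- **Outpatient and follow-up:** samples are taken twice weekly in treatment and again at follow-up, "using on-site TESTCUP5 Drug Screen (Roche Diagnostics Inc., Totowa, NJ) to monitor opiate and other drug use". The content of the kit is given as "The TestCup5 kit provides results for opioids, cocaine, THC, PCP and barbiturates".
- **Breath:** "breath alcohol levels will also be assessed with the Alcosensor III Intoximeter at each face-to-face contact, 2 times weekly".

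Three other places draw on urine when drinking is the question.

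- **Relapse definition (Section V.3, in the text after the counseling description under Admission):** the first day of any alcohol use, "as documented by self-report and/or positive urine and positive breathalyzer for alcohol".
- **Primary outcomes (Section V.12):** heavy drinking days and any drinking days are taken from daily smartphone or telephone surveys, and "also with weekly urine drug screens/breathalyzer reports and self report of drug use on the Substance Use Calendar".
- **Concordance (Section VI.A.3, Source, in the outpatient procedures):** "Concordance between daily IVR or MetricWire reports and alcohol positive urines will be evaluated for daily versus retrospective reporting".

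Two general statements rest on the same premise. General Procedures in Section V.3 has breath and urine testing confirm self-reported drug and alcohol use, and item a of Section VIII says the same of urine and breathalyzer data.

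**The concern.** The plan treats outpatient urine as a source of evidence on alcohol, but the only outpatient kit it describes is for other drugs. If the kit is used as described, no outpatient urine can come back positive for alcohol.

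A planned analysis would then have an empty reference variable. A rule meant to let a biological test establish relapse would never operate. A reader of the results could also believe that outpatient drinking was checked by two biological tests when it was checked by one.

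The case that matters most is the participant who denies drinking but has a positive breath test. That is where objective evidence is worth having, and the relapse rule as worded sets it aside. The Data Analytic Procedures in Section V.12 give no rule for sources that disagree, so nothing there repairs it.

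**Working it through.** The plan gives no figure to reproduce on this point. The check sets the kit's analytes against each use of urine and asks what still works when outpatient urine is never alcohol-positive.

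**Inputs**

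- Kit analytes (Section V.3): 5 listed, of which alcohol: 0.
- Other outpatient urine alcohol assays described: none.
- Scheduled outpatient breath tests (Section V.3): 2 per week.

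**1. Concordance analysis.** It compares the daily report with alcohol-positive urine. For outpatients the second variable has no positive values by construction, so agreement on positives cannot be estimated. The analysis fails as written.

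**2. Relapse definition.** Let S be self-reported drinking, U a urine positive for alcohol and B a positive breathalyzer. Read literally, taking the alcohol qualifier to cover both tests:

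relapse = S or (U and B)

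With U always negative, (U and B) is always false, so relapse = S. The breath result never changes the classification:

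| S | B | Relapse as worded (U never positive) | Relapse as S or B |
|---|---|---|---|
| yes | positive | yes | yes |
| yes | negative | yes | yes |
| no | positive | **no** | **yes** |
| no | negative | no | no |

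The two rules differ in one row only: denied drinking with a positive breath test.

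**3. Primary outcomes.** Four sources are listed: daily survey, Substance Use Calendar, breathalyzer and urine drug screen. Without urine, three remain that bear on alcohol. Both outcomes can still be computed; urine contributes nothing to them.

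**4. Breath-test coverage, for context.** Scheduled tests over 12 outpatient weeks: 2 × 12 = 24, in 12 × 7 = 84 days, and 24/84 = 28.6%. For a 9-week outpatient phase: 2 × 9 = 18 in 63 days, again 28.6%. This is the scheduled count, not a maximum.

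**5. Frequency.** Section V.12 describes the urine and breath reports as weekly; Section V.3 has both twice weekly.

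Of the three uses of urine, one fails outright for outpatients, one fails in its biochemical limb, and one loses a source that the others can cover.

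**The case against.** The strongest reply is that little depends on this. The primary outcomes come first from daily surveys, with the calendar and breathalyzer behind them, and Section V.12 speaks of urine drug screens without mentioning alcohol-positive urine. Relapse is not a listed primary or secondary outcome, and its definition still works through self-report. All of this stands. A reader might infer that the primary outcomes cannot be computed, or have no objective check at all. The documents do not support that: breath tests are taken at every face-to-face contact.

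The relapse wording can also be read loosely, as naming urine and breath as two separate sources. On that reading a positive breath test alone would suffice. This is possible, but the literal text joins the two tests with a conjunction, and a definition should not depend on which reading the analyst picks.

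A third reply is that the intake, inpatient and general statements suggest a urine alcohol test was intended somewhere. The intake and inpatient assays are indeed not itemised, so nothing shows that they lack alcohol, and the finding must stop at outpatient and follow-up samples. For those, the plan names the kit and its contents.

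Finally, it is tempting to say that the kit leaves 60 of 84 days (71%) on self-report alone. That does not follow from this defect. Urine is collected on the same twice-weekly schedule, so the count of sampling days would be the same with a kit that tested for alcohol. More frequent appointments are allowed for participants who keep drinking, and those on the inpatient-outpatient plan spend 3 to 4 of the weeks on the unit.

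**Conclusion.** The inconsistency is real and limited to outpatient and follow-up urine. As written, the concordance analysis cannot be run in outpatients. The biochemical limb of the relapse definition, read literally, cannot be met, so relapse there reduces to self-report and a positive breath test with denied drinking is lost. Urine adds nothing to verification of the outpatient drinking outcomes, which rest on daily surveys, the calendar and breath tests scheduled twice weekly.

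The size is 0 alcohol analytes out of 5 listed, and one of four possible self-report and breath combinations misclassified. How many participants fall in that combination cannot be derived from the documents.

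The conclusion assumes that the named kit is the only urine test used in outpatients and at follow-up, and that the relapse wording is taken literally. It does not extend to intake or inpatient urine, and it does not make the primary outcomes uncomputable. It is worth correcting because a stated analysis and a stated rule fail for outpatients and the remedy uses data already collected.

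**What to change.** For outpatient and follow-up samples only:

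- **Section V.3, relapse definition:** define relapse as self-reported drinking or a positive breathalyzer, with an explicit or.
- **Section V.12, primary outcomes:** count a day with a positive breathalyzer as an any-drinking day even if drinking is denied. Keep heavy drinking days on reported drink counts, because that outcome is defined by number of drinks (5 or more for men, 4 or more for women) and a breath test gives no count. Drop urine as evidence of drinking, and reconcile the weekly frequency with the twice-weekly schedule in Section V.3.
- **Section VI.A.3, concordance:** compare daily survey, Substance Use Calendar and breathalyzer.
- **Section V.3, General Procedures, and Section VIII, item a:** align the statements on what urine confirms.

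Leave intake and inpatient urine in place, since their assays are not itemised. If a urine alcohol assay was in fact intended for outpatients, naming it would remove the contradiction, but the relapse conjunction would still need rewording so that a positive breath test can count on its own.

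The cost is protocol and analysis-plan wording, and a weaker claim of objective verification. No new data collection is needed, and sample size, power and alpha are unchanged.
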